4.2 Discussion of Study Design

Choice of Control Group

Placebo plus glucocorticoid taper (with taper duration dependent on baseline dose of glucocorticoid) has been selected as the appropriate control group to evaluate the primary efficacy endpoints as double-blind, placebo-controlled study designs are generally acknowledged as standard for unbiased estimates of treatment differences. The control group in this study will follow the same glucocorticoid

taper as the ABBV-154 treatment groups. Subjects are allowed to use glucocorticoid rescue if a PMR flare is confirmed, which is consistent with standard of care for PMR relapse.

Appropriateness of Measurements

Standard statistical, clinical, and laboratory procedures will be utilized in this study. The key efficacy measures in this study are standard for assessing disease activity in subjects with PMR. Additional exploratory efficacy measures were added in response to an unmet need for outcome assessments relevant to the PMR population based on literature review and consultation with PMR experts. Safety related measures, including clinical and laboratory procedures, in this study are standard and generally accepted for this study population.

Suitability of Subject Population

This study will enroll adult female and male subjects who are at least 50 years of age and have been diagnosed with PMR.¹⁵ The study population is considered glucocorticoid-dependent. ABBV-154 has the potential to improve disease activity in PMR subjects while avoiding glucocorticoid-associated toxicity often seen with systemic glucocorticoids. While this is the first study to test ABBV-154 in PMR, safety results of ABBV-154 did not identify any unexpected risk or trend in the healthy volunteer population.

Selection of Doses in the Study

The dose selection in this study was informed by the safety, efficacy, PK, and pharmacodynamic results from a related ADC with the same mechanism of action (ABBV-3373) in a Phase 2a proof-of-concept study in bio-naïve RA subjects on background methotrexate, in which ABBV-3373 demonstrated superiority over adalimumab based on comparison to a prespecified historical adalimumab mean.

The 3 SC dosing regimens (40 mg EOW, 150 mg EOW, and 340 mg EOW) selected for evaluation in this study are reasonably separated across a wide dose range to cover the potential clinical efficacious doses and to enable a robust characterization of dose-/exposure-response relationships for Phase 3 dose selection. All selected doses are within the range of single doses safely tested in the ABBV-154 first-in-human study (highest dose 600 mg intravenous) and are adequately covered by safety margins provided by chronic toxicology studies. Projected ABBV-154 and payload safety margins for the high dose of 340 mg SC EOW are at least 24-fold and 10-fold, respectively, based on predicted ABBV-154 human exposures and the observed toxicokinetic data in the 26-week cynomolgus monkey study.

5 STUDY ACTIVITIES

5.1 Eligibility Criteria

Subjects must meet all of the following criteria in order to be included in the study. Anything other than a positive response to the questions below will result in exclusion from study participation. Additional information on screening (including re-screening) can be found in the Operations Manual ([Appendix H](#)).

Consent

- ✓ 1. Subjects must be able to understand and willing to adhere to all protocol requirements and voluntarily sign and date an informed consent, approved by an independent ethics committee (IEC)/institutional review board (IRB), prior to the initiation of any screening or study-specific procedures.

Demographics and Laboratory Assessments

- ✓ 2. Adult **male or female, at least 50 years** of age at the time of screening.
- ✓ 3. Body mass index (BMI) is ≥ 18.0 to ≤ 39.9 kg/m² after rounding to the nearest tenth. BMI is calculated as weight in kg divided by the square of height measured in meters.
- ✓ 4. **Laboratory values** must meet the following criteria within the Screening Period prior to the first dose of study drug:
 - Serum aspartate aminotransferase (AST) $\leq 2.5 \times$ ULN;
 - Serum alanine transaminase (ALT) $\leq 2.5 \times$ ULN;
 - Estimated glomerular filtration rate (GFR) by simplified 4-variable Modification of Diet in Renal Disease (MDRD) formula ≥ 30 mL/min/1.73 m²;
 - Absolute neutrophil count (ANC) $\geq 1,500/\mu\text{L}$;
 - Absolute lymphocyte count $\geq 800/\mu\text{L}$;
 - Platelet count $\geq 75,000/\mu\text{L}$;
 - Glycated hemoglobin (HbA1c) $\leq 8.5\%$;
 - Serum potassium > 3.0 mmol/L and < 5.5 mmol/L; and
 - Thyroid-stimulating hormone (TSH) < 10 mIU/L.
- ✓ 5. Subject must have a negative test result for anti-citrullinated protein (anti-CCP) at Screening.

Disease Activity

- ✓ 6. Clinical diagnosis of PMR and fulfillment of the 2012 EULAR/ACR provisional classification criteria for PMR (see [Appendix D](#)).¹⁵ If utilizing the optional ultrasound criteria, ultrasound must have been assessed by a qualified physician experienced in musculoskeletal ultrasound.
- ✓ 7. Following a confirmed diagnosis of PMR, subject must have shown a clinical response to prednisone (or equivalent).
- ✓ 8. Subject must have had at least 2 episodes of unequivocal PMR flare while attempting to taper prednisone, with the dose of prednisone (or equivalent) at the time of flare ≥ 5 mg/day, prior to Baseline; the most recent flare must have been within 24 weeks of Baseline. Unequivocal PMR flare is defined as clinical signs and symptoms of PMR (shoulder and/or hip girdle pain with inflammatory stiffness, neck pain with inflammatory stiffness, or new or worsened limited range of motion of hips and/or shoulders) that resulted in an increase in glucocorticoid dose.

- ✓ 9. Subject must not exhibit clinical signs and symptoms of PMR (shoulder and/or hip girdle pain with inflammatory stiffness, neck pain with inflammatory stiffness, or new or worsened limited range of motion of hips and/or shoulders) within 2 weeks of Baseline.

Subject History

- ✓ 10. Subject is judged to be in good health as determined by the Principal Investigator, based upon the results of medical history, laboratory profile, physical examination, chest x-ray (CXR), and a 12-lead ECG performed during Screening.
- ✓ 11. No history of an allergic reaction or significant sensitivity to constituents of the study drug (and its excipients) and/or other products in the same class. No history of anaphylactic reaction to any agent (e.g., food products and bee sting); or a reaction to any immunoglobulin G (IgG) containing product.
- ✓ 12. Subject must have no current or past history of infection including:
 - Active tuberculosis (TB) or meets TB exclusionary parameters (specific requirements for TB testing are provided in the Operations Manual);
 - Subjects **in Japan** only: Positive result of beta-D-glucan (screening for *Pneumocystis jirovecii* infection) or two consecutive indeterminate results of beta-D-glucan during the Screening Period.
 - Human Immunodeficiency virus (HIV) infection defined as confirmed positive anti-HIV antibody (HIV Ab) test;
 - Active infection(s) requiring treatment with intravenous anti-infectives within 30 days, or oral/intramuscular anti-infectives within 14 days prior to the first dose of study drug;
 - Chronic recurring infection and/or active viral infection that, based on the investigator's clinical assessment, makes the subject an unsuitable candidate for the study;
 - Confirmed COVID-19: the Baseline Visit must be at least 21 days from onset of signs/symptoms or positive SARS-CoV-2 test; symptomatic subjects must have recovered, defined as resolution of fever without use of antipyretics and improvement in symptoms;
 - Suspected COVID-19: subjects with signs/symptoms suggestive of COVID-19, known exposure, or high-risk behavior should undergo molecular (e.g., polymerase chain reaction [PCR]) testing to rule out SARS-CoV-2 infection or must be asymptomatic for 14 days from a potential exposure;
- ✓ 13. Subjects must not have evidence of:
 - Hepatitis B virus (HBV): hepatitis B surface antigen (HBs Ag) positive (+) test or detectable HBV deoxyribonucleic acid (DNA) PCR qualitative test for subjects who are hepatitis B core antibody (HBc Ab) positive (+) (and for hepatitis B surface antibody [HBs Ab] positive (+) subjects where mandated by local requirements);
 - Hepatitis C virus (HCV): detectable HCV ribonucleic acid (RNA) in any subject with anti-HCV antibody (HCV Ab).
- ✓ 14. Subjects must not have any of the following medical diseases or disorders:

- Suspected or confirmed adrenal insufficiency;
 - Hypothyroidism for which the subject is not receiving physiologic replacement therapy;
 - History of moderate to severe congestive heart failure (New York Heart Association Class III or IV);
 - Uncontrolled hypertension defined as confirmed systolic blood pressure >160 mm Hg or diastolic blood pressure > 100 mmHg at rest despite treatment;
 - History of an organ transplant that requires continued immunosuppression;
 - Recent (within past 6 months) cerebrovascular accident, myocardial infarction, coronary stenting, and/or aorto-coronary bypass surgery;
 - History of GCA (based on clinical, ultrasound, and/or temporal artery biopsy diagnosis) or active symptoms (e.g., headache, temporal artery or scalp tenderness, jaw claudication, visual signs or symptoms, new or worsened extremity claudication) suggestive of GCA, per the investigator's judgement;
 - History of systemic lupus erythematosus, systemic sclerosis, inflammatory myopathies;
 - Active fibromyalgia;
 - History of inflammatory arthritis (including but not limited to rheumatoid arthritis, psoriatic arthritis, etc.). A history of gout is permitted if subject has been both on stable (non-glucocorticoid) suppressive therapy and without flares for at least two years prior to Baseline and is expected to remain on this therapy through the end of study drug administration;
 - History of glaucoma, osteonecrosis or osteoporosis with high risk of fracture (e.g., T-score ≤ -2.5 with history of fragility fracture);
 - History of demyelinating disease (including myelitis) or neurologic symptoms suggestive of demyelinating disease;
 - Active or suspected malignancy or history of any malignancy within the last 5 years, except for successfully treated nonmelanoma skin cancer (NMSC) or localized carcinoma in situ of the cervix. Regardless of the time since remission, subjects with any history of lymphoma, leukemia, melanoma, or Merkel cell carcinoma;
 - History of any medical condition other than PMR that is likely to require systemic glucocorticoid treatment during the study (e.g., asthma and chronic obstructive pulmonary disease [COPD] per investigator judgement). Inhaled glucocorticoids are allowed for stable medical conditions but must be at stable dose ≥ 4 weeks prior to Baseline.
- ✓ 15. Subject must not have a history of clinically significant (per investigator's judgment) drug or alcohol abuse within the 12 months prior to Baseline.

- ✔ 16. There must be no reason the investigator believes that the subject is an unsuitable candidate to participate in the study, receive study drug, or would be placed at risk by participating in the study. France only: Subjects must be registered with a social security scheme. Subjects may not fall within the scope of Article L1121-6 of the French Public Health Code (persons deprived of their freedom further to a judicial or administrative decision, persons receiving psychiatric care and persons admitted to a health and social facility for reasons unrelated to the study) or Article L1121-8 (adults under a legal protection order or unable to express their consent).
- ✔ 17. Wearable Device Substudy only: Subjects must not have a history of pre-existing sleep disorders, including insomnia, obstructive sleep apnea, restless leg syndrome or currently on prescription sleep medications to participate in the sleep assessment portion of the study. Subjects with these histories may participate in the study as a whole if all other eligibility criteria are met.

Contraception

- ✔ 18. For all females of child-bearing potential: must not have a **positive serum pregnancy test** at the Screening Visit and must have a negative urine pregnancy test at Baseline, prior to the first dose of study drug (local practices may require serum pregnancy testing at Baseline). Subjects with a borderline serum pregnancy test at Screening must have absence of clinical suspicion of pregnancy or other pathological causes of borderline results and a serum pregnancy test ≥ 3 days later to document continued lack of a positive result (unless prohibited by local requirements).
- ✔ 19. Female subjects of childbearing potential must practice at least 1 protocol-specified **method of birth control**, that is highly effective from Study Day 1 through at least 70 days after the last dose of study drug (local practices may require 2 methods of birth control) (refer to Section 5.2 for more detail on contraception). Female subjects of non-childbearing potential do not need to use birth control. For France and the United Kingdom (UK) only: Female subjects of childbearing potential must practice at least 1 protocol-specified **method of birth control**, that is highly effective from Study Day 1 through at least 150 days after the last dose of study drug.
- ✔ 20. Females must not be **pregnant, breastfeeding, or considering becoming pregnant** and may not donate eggs during the study or for approximately 70 days (150 days for France and UK only) after the last dose of study drug.
- ✔ 21. **If male**, and subject is **sexually active with a female partner(s) of childbearing potential**, he must agree, from Study Day 1 through 70 days (150 days for UK only) after the last dose of study drug, to practice the protocol-specified contraception.
- ✔ 22. If male, must not be considering **fathering a child or donating sperm** during the study or for approximately 70 days (150 days for UK only) after the last dose of study drug.

Concomitant Medications

- ✔ 23. Subject must be on a stable prednisone (or equivalent) dose of 5 to 15 mg/day for ≥ 2 weeks prior to Baseline. Subjects may be on up to 25 mg/day at the Screening Visit provided that the subject is able to taper to 15 mg/day or less, with a stable dose ≥ 2 weeks prior to Baseline.

- ✓ 24. Subject must be willing to follow the protocol-defined glucocorticoid tapering regimen.
- ✓ 25. Subject must not have been treated with a prior TNF antagonist (adalimumab, etanercept, infliximab, certolizumab, golimumab).
- ✓ 26. Subject must not have prior exposure to ABBV-154.
- ✓ 27. Subject must have **discontinued use of immunomodulators other than prednisone (or equivalent) and hydroxychloroquine** prior to Baseline. Subject who is on current treatment with concomitant hydroxychloroquine must be on continuous treatment for ≥ 12 weeks and at stable dose (≤ 400 mg/day) for ≥ 4 weeks prior to Baseline and expected to remain on stable dose through the end of study drug administration. Prior to Baseline, subjects who need to discontinue immunomodulators to comply with this criterion are required to adhere to the washout periods specified below or at least 5 times the mean terminal elimination half-life of a drug. No minimum washout prior to Baseline is required for a biologic therapy if an undetectable drug level measured by a commercially available assay is documented.
 - ≥ 1 week for anakinra;
 - ≥ 4 weeks for methotrexate, sulfasalazine, hydroxychloroquine, cyclosporine, tacrolimus, bucillamine, iguratimod, azathioprine, mycophenolate, tocilizumab, sarilumab, and JAK inhibitors (upadacitinib, tofacitinib, baricitinib, filgotinib, ruxolitinib, peficitinib);
 - ≥ 8 weeks for leflunomide if no elimination procedure was followed, or adhere to an elimination procedure (i.e., 11 days with cholestyramine or activated charcoal or as per local label);
 - ≥ 8 weeks for abatacept;
 - ≥ 6 months for cyclophosphamide and other alkylating agents;
 - ≥ 1 year for rituximab OR ≥ 6 months if B cells have returned to pretreatment level or normal reference range (local lab) if pretreatment levels are not available.
- ✓ 28. Subject must not have been treated with any intra-articular, intramuscular, intravenous, trigger point or tender point, intra-bursa, tendon sheath, or epidural glucocorticoids in the preceding 8 weeks prior to Baseline. Subjects must not have been treated with oral glucocorticoids for non-PMR reasons within 8 weeks prior to Baseline.
- ✓ 29. Subject must not have been treated with super-high potency and/or high potency topical glucocorticoids (see [Appendix E](#)) in the preceding 1 week prior to Baseline.
- ✓ 30. Subject must not have been treated with **any investigational drug** within 30 days or 5 half-lives of the drug (whichever is longer) prior to Baseline or is currently enrolled in another interventional clinical study or was previously enrolled in this study.
- ✓ 31. Subject must not have received **any live vaccine** within 4 weeks (or longer if required locally) prior to Baseline, or expected need of live vaccination during study participation including at least 70 days after the last dose of study drug.

- ✓ 32. Subject must have discontinued all opioid and analgesic medications with the exception of nonsteroidal anti-inflammatory drugs (NSAIDs), acetaminophen, tramadol, combination of acetaminophen with codeine, or combination of acetaminophen with hydrocodone \geq 1 week prior to Baseline. Subjects entering on analgesics must be on stable dose \geq 1 week prior to Baseline.
- ✓ 33. Subjects must not have been treated with oral traditional Chinese medicine within 4 weeks prior to Baseline.

5.2 Contraception Recommendations

Contraception recommendations related to use of concomitant therapies prescribed should be based on the local label.

Contraception Requirements for Females

Subjects must follow the following contraceptive guidelines as specified:

- Females, Non-Childbearing Potential

Females do not need to use birth control during or following study drug treatment if considered of non-childbearing potential due to meeting any of the following criteria:

1. Premenopausal female with permanent sterility or permanent infertility due to one of the following:
 - Permanent sterility due to a hysterectomy, bilateral salpingectomy, bilateral oophorectomy
 - Nonsurgical permanent infertility due to Mullerian agenesis, androgen insensitivity, or gonadal dysgenesis; investigator discretion should be applied to determining study entry for these individuals.
2. Postmenopausal female
 - Age $>$ 55 years with no menses for 12 or more months without an alternative medical cause.
 - Age \leq 55 years with no menses for 12 or more months without an alternative medical cause AND a follicle-stimulating hormone (FSH) level \geq 30 IU/L.

- Females, of Childbearing Potential

- Females of childbearing potential must avoid pregnancy while taking study drug(s) and for at least 70 days (150 days for France and UK only) after the last dose of study drug.
- Females must commit to one of the following methods of birth control:
 - Combined (estrogen and progestogen containing) hormonal birth control (oral, intravaginal, transdermal, injectable) associated with inhibition of ovulation-initiated at least 30 days prior to Study Day 1 (Baseline Visit).
 - Progestogen-only hormonal birth control (oral, injectable, implantable) associated with inhibition of ovulation initiated at least 30 days prior to Study Day 1 (Baseline Visit).

- Bilateral tubal occlusion/ligation (can be via hysteroscopy, provided a hysterosalpingogram confirms success of the procedure).
- Intrauterine device (IUD).
- Intrauterine hormone-releasing system (IUS).
- Vasectomized partner (provided the partner has received medical confirmation of the surgical success of the vasectomy and is the sole sexual partner of the trial subject).
- Practice true abstinence, defined as: Refraining from heterosexual intercourse when this is in line with the preferred and usual lifestyle of the subject (periodic abstinence [e.g., calendar, ovulation, symptothermal, post-ovulation methods] and withdrawal are not acceptable).

If required per local practices, male or female condom with or without spermicide OR cap, diaphragm or sponge with spermicide should be used in addition to one of the birth control methods listed above(excluding true abstinence).

Contraception Requirements for Males

Male subjects who are sexually active with a female partner of childbearing potential, must agree to use male condoms, even if the male subject has undergone a successful vasectomy, from Study Day 1 through at least 70 days (150 days for UK only) after the last dose of study drug.

5.3 Prohibited Medications and Therapy

Subjects must be able to safely discontinue any prohibited medications as specified in Section 5.1 and Section 5.4. Subjects must be consented for the study prior to discontinuing any prohibited medications for the purpose of meeting study eligibility.

Intra-articular, intra-bursal, tendon sheath, trigger point or tender point, or epidural administration of glucocorticoids are not permitted prior to Week 24.

The following medications are prohibited through the end of study drug administration:

1. Systemic glucocorticoids (including but not limited to oral, intravenous, intramuscular), except as permitted as outlined in Section 5.1, Section 5.4, and Section 5.8.
2. Super-high potency and high potency topical glucocorticoids (see Appendix E).
3. Corticotropin gel injection (i.e., Acthar®)
4. Biologic Therapies: Subjects must have discontinued biologic therapies prior to the first dose of study drug as specified in the washout procedures (Eligibility Criterion 27 in Section 5.1). For all other biologic therapies, the required washout period is at least five times the mean terminal elimination half-life of the medication prior to Baseline. No minimum washout prior to Baseline is required for a biologic therapy if an undetectable drug level measured by a commercially available assay is documented. Therapies including but not limited to the following biologic therapies are prohibited medications through the end of study drug administration:

- Abatacept
 - Adalimumab
 - Anakinra
 - Belimumab
 - Certolizumab
 - Dupilumab
 - Etanercept
 - Golimumab
 - Infliximab
 - Ixekizumab
 - Natalizumab
 - Rituximab
 - Risankizumab
 - Sarilumab
 - Secukinumab
 - Tocilizumab
 - Ustekinumab
 - Vedolizumab
5. Conventional and targeted synthetic disease-modifying antirheumatic drugs (DMARDs):
Subjects must have discontinued conventional and targeted synthetic DMARD therapies prior to Baseline as specified in the washout procedures (see Eligibility Criteria in Section 5.1), except for hydroxychloroquine. For all other conventional or targeted synthetic DMARDs, the required washout period is at least five times the mean terminal elimination half-life of the medication prior to Baseline.
 6. Investigational drugs.
 7. Live vaccination (see Section 5.4 for examples of live vaccines).
 8. Any opiate analgesics with the exception of tramadol, combination of acetaminophen with codeine, or combination of acetaminophen with hydrocodone.
 9. Traditional oral Chinese medicine (e.g., tripterygium glycosides, sinomenine, total glucosides of white peony).

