5.4 Prior and Concomitant Therapy

Any medication or vaccine (including over-the-counter or prescription medicines, vitamins, and/or herbal supplements) that the subject is receiving at the time of enrollment or receives during the study must be recorded on the appropriate electronic case report form (eCRF) from 30 days prior to Baseline

through the 70-day Post-treatment Follow-up Visit. Also, medications taken for PMR since the date of diagnosis and any glucocorticoids (based on subject's recollection and available medical records) should be entered into the appropriate eCRF inclusive of the dates of first and last dose, dosage, route of administration and reason for discontinuation, if known.

Information regarding potential drug interactions with ABBV-154 can be located in the ABBV-154 Investigator's Brochure.¹⁴

Subjects should receive oral calcium and 25-hydroxy vitamin D and/or other therapy for prevention of glucocorticoid-induced osteoporosis in accordance with local standard-of-care practice, unless contraindicated, at the discretion of the investigator. Study participants with documented osteoporosis should be treated with approved drugs for osteoporosis according to local standard-of-care practice or clinical guidelines (e.g., National Osteoporosis Foundation or Japanese Society for Bone and Mineral Research).

See Section 5.8 for concomitant glucocorticoid treatment and rescue treatment for PMR flare.

Vaccines

If the subject and investigator choose to receive/administer live vaccines, these vaccinations must be completed (per local label) at least 28 days (or longer if required locally) before first dose of study drug. Live vaccinations are prohibited during study participation, including at least 70 days after the last dose of study drug. Examples of live vaccines include, but are not limited to, the following:

- Monovalent live influenza A (H1N1) (intranasal);
- Seasonal trivalent live influenza (intranasal);
- Zostavax (herpes zoster, live attenuated);
- Rotavirus;
- Varicella (chicken pox);
- Measles-mumps-rubella or measles-mumps-rubella-varicella;
- Oral polio vaccine;
- Smallpox;
- Yellow fever;
- Bacille Calmette-Guérin (BCG);
- Typhoid (oral).

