5.8 Study Drug

ABBV-154 and Matching Placebo

ABBV-154 and matching placebo will be manufactured and provided by AbbVie (Table 1). Each dose will be administered by a healthcare professional as 3 SC injections (2 prefilled syringes [PFS] with 1.5 mL fill volume and 1 PFS with 0.4 mL fill volume) in the abdomen or thigh. Blinded study drug will be administered EOW at approximately the same time of day, preferably between 7 and 11 a.m., beginning on Day 1 (Baseline Visit). The study drug can be taken with or without food. A 15- to 30-minute observation period is required after each dose. The last dose of ABBV-154/placebo will be given at Week 50.

ABBV-154 and matching placebo syringes will be packaged in cartons with quantities sufficient to accommodate the study design. Each prefilled syringe and carton will be labeled per local requirements and these labels must remain affixed to the syringe and carton. Upon receipt, study drug should be stored as specified on the label (refrigerated at 2 to 8°C) and kept in a secure location. Each kit will contain a unique kit number. This kit number is assigned to a subject via Interactive response technology (IRT) and encodes the appropriate study drug to be dispensed at the subject's corresponding study visit. Study drug must not be dispensed without contacting the IRT system. Site staff will complete all blank spaces on the label before dispensing study drug for the subject. Study drug is for investigational use only and will only be used for the conduct of this study.

Table 1. Investigational Product

Study Drug	Dosage Form	Strength	Route of Administration	Manufacturer
ABBV-154	Solution for Injection/infusion in PFS	40 mg 150 mg	subcutaneous	AbbVie
Placebo for ABBV-154	Solution for Injection/infusion in PFS	Not applicable	subcutaneous	AbbVie

PFS = prefilled syringe

Glucocorticoids

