### **10.2.1 Treatment-Emergent Adverse Events**

Treatment-emergent AEs are defined as any AE with the onset that is after the first dose of study drug and with an onset date no more than 5 half-lives of the study drug (i.e., 70 days). Events where the onset date is the same as the study drug start date are assumed to be treatment-emergent, unless the study drug start time and the AE start time are collected and the AE start time is prior to the study drug start time. All treatment-emergent AEs will be summarized overall, as well as by primary MedDRA SOC and Preferred Term. The SOCs will be presented in alphabetical order, and the PTs will be presented in alphabetical order within each SOC.

The number and percentage of subjects experiencing treatment-emergent AEs will be summarized.

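### Protocol Section 5.3 ends the live-vaccine ban when study drug ends, while Section 5.4 and criterion 31 carry it at least 70 days past the last dose

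*Protocol*

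**What the plan says.** Section 5.3 of the protocol puts one lead-in over its whole numbered list: "The following medications are prohibited through the end of study drug administration". Item 7 of that list is "Live vaccination (see Section 5.4 for examples of live vaccines"; it says nothing about duration.

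The vaccine paragraph of Section 5.4 sets a longer period: "Live vaccinations are prohibited during study participation, including at least 70 days after the last dose of study drug". Criterion 31 in Section 5.1 applies the same horizon at entry, by ruling out a subject with an "expected need of live vaccination during study participation including at least 70 days after the last dose of study drug".

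Two statements fix the timing. Section 5.8 says "The last dose of ABBV-154/placebo will be given at Week 50". SAP Section 10.2.1 limits treatment-emergent events to an onset "no more than 5 half-lives of the study drug (i.e., 70 days", so the SAP treats 70 days as five half-lives.

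**The concern.** One product has two end dates in adjacent sections. Section 5.3 is the natural place for a site to look up what is banned, and its date is the shorter one. A coordinator who checks only that list would conclude that the restriction lapses with the last injection.

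Section 2.2 of the protocol names serious infection as a risk of both TNF antagonists and glucocorticoids. A live vaccine given while drug is still present is the situation that the longer window covers. Subjects are at least 50 years old, and a live zoster vaccine is among the examples in 5.4, so the question could arise in practice.

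There is a smaller consequence for reporting. SAP Appendix A counts subjects who took a banned concomitant medication but does not say which section defines the banned period.

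**Working it through.** **Side by side**

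| Place | When the restriction ends |
|---|---|
| 5.3, item 7 | End of study drug administration |
| 5.4, Vaccines | Covers study participation and at least 70 days after the last dose |
| 5.1, criterion 31 | Same period as 5.4, applied to expected need at entry |

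Item 1 of the 5.3 list (systemic glucocorticoids) imports exceptions from Sections 5.1, 5.4 and 5.8. Item 7 has no comparable wording on duration and takes only examples from 5.4. On its face, item 7 therefore keeps the lead-in's end date.

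**Length of the gap**

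- Planned completer: last dose at Week 50. Section 5.3 ends at Week 50; 5.4 runs to at least Week 50 + 70/7 = Week 60. The gap is 70 days.
- Alternative reading: Sections 4.1 and 5.8 in places count sponsor-supplied prednisone/prednisolone as study drug, and a subject on rescue may take it up to Week 52. The gap is then 70 − 14 = 56 days for those subjects.
- Early discontinuer who stays in the study, as Section 5.6 encourages. For illustration, drug stops at Week 4 and the subject is followed to Week 52. Section 5.3 ends at Week 4, while 5.4 read literally covers all participation. The gap is 52 − 4 = 48 weeks.

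**Exposure left in the gap**

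The documents give no separate half-life, so the 70 days cannot be reproduced independently. Solving 5 × half-life = 70 gives 14 days. The rationale for contraception in protocol Appendix G, used here as context only, says 70 days exceeds five times the upper limit of the mean half-life, so 14 days is an upper-end value. Half-lives of 7 and 10 days are my assumptions to show the range below it.

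Model: fraction of last-dose peak remaining at day t = 2^(−t/h), with h the half-life. This is one-compartment decay that ignores subcutaneous absorption.

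| Day after last dose | h = 7 (assumed) | h = 10 (assumed) | h = 14 (SAP) |
|---|---|---|---|
| 1 | 90.6% | 93.3% | 95.2% |
| 14 | 25.0% | 37.9% | 50.0% |
| 28 | 6.2% | 14.4% | 25.0% |
| 70 | 0.1% | 0.8% | 3.1% |

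For example, at day 28 with h = 14, 2^(−28/14) = 2^(−2) = 25%. Dosing is every other week, so day 14 is when the next injection would have been due; exposure there equals the usual on-treatment trough.

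**Who is exposed**

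Randomization is 1:1:1:1 with 40 per arm. Residual ABBV-154 is possible in 3 × 40 = 120 of the 160 planned subjects; the other 40 receive placebo.

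**The case against.** The strongest reply is that nothing in 5.3 authorises a live vaccine. It stops listing one. Two bans of different length can both be obeyed by keeping the longer, and 5.4 is the specific vaccine rule and is unqualified. The pointer in item 7 also leads to the paragraph that holds the 70-day sentence, directly before the examples. This stands, and it lowers the practical risk. It does not remove the conflict, because a site that already knows which vaccines are live has no reason to follow a pointer offered for examples.

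A reader might go further and infer any of the following. The documents do not support them.

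- *The protocol lets sites vaccinate at near-full exposure.* Section 5.3 lapses rather than permits. High residual exposure describes only the first days after the last dose, under an assumed decay model. By day 14 it is at most half of peak.
- *All 160 subjects are at risk from residual drug.* Forty receive placebo. Criterion 31 also excludes anyone with an expected need for a live vaccine in the period.
- *Section 5.6 frees early discontinuers from the ban.* It leaves their care to the investigator's clinical judgment, but does not mention vaccines or lift 5.4.
- *The same vaccination would count as a deviation at one site and not at another.* Section 5.4 already makes it a deviation wherever it occurs in the window. Appendix A is silent on the source of the period, which is a reason to state it but is not evidence of unequal treatment.

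**Conclusion.** The contradiction is in the current text and does not depend on the summary of changes. Section 5.3 read alone ends the live-vaccine restriction about 70 days before 5.4 does after the last planned dose (56 days on one reading for subjects still on sponsor-supplied prednisone/prednisolone at Week 52). The gap may be far longer for early discontinuers who remain in follow-up.

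In the ABBV-154 arms, about 25–50% of last-dose peak exposure would remain at day 14 and 6–25% at day 28. These figures rest on simple decay and a half-life between 7 days (assumed) and 14 days (implied by the SAP); the documents contain no concentration data to test them.

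How often the conflict would matter cannot be estimated, because no expected number of live vaccinations is given and criterion 31 should keep it low. No endpoint, estimand or efficacy analysis is affected. The point is worth correcting because it concerns subject safety and costs almost nothing to resolve.

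**What to change.** Reconcile item 7 of Section 5.3 with Section 5.4 and criterion 31 so that one duration for live vaccination appears in all three places. The sponsor's medical team sets that duration, including how it applies to subjects who stop drug early and stay in the study. Once it is set, item 7 can either state its own duration or refer to 5.4 for duration as well as for examples.

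Specify in SAP Appendix A that the check for banned concomitant medication uses the same duration for live vaccines.

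The cost is one line in Section 5.3, or a clarification letter to sites, plus one clause in the SAP. Data collection does not change: Section 5.4 already has vaccines recorded through the 70-day follow-up visit.
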